8.1. Adverse events

In addition to the pre-specified safety outcomes, participants will be asked about any adverse events occurring or worsening since the time of infusion. An *adverse event* will be defined as

Study Name: The Fragility Fracture Trial
Version No: 2
Date: 2020-10-04
EudraCT No: 2019-004766-17

is done by the International Conference on Harmonisation of Technical Requirements for Registration of Pharmaceuticals for Human Use (ICH):⁵⁰

Any untoward medical occurrence in a patient or clinical investigation subject administered a pharmaceutical product and which does not necessarily have to have a causal relationship with this treatment.

The principal investigators or research nurses will interview participants about adverse events at each study contact. The questions will be open-ended, instead of directed at particular types of events. Participants will also have the possibility of reporting adverse events between the scheduled contacts. Participants who withdraw will be asked if they wish to answer questions about adverse events before they formally withdraw.

The following information will be collected about adverse events:

1. Type of event (diagnosis, symptom(s), or abnormal laboratory value)
2. Duration (start date and, if applicable, stop date)
3. Causality (suspected/not suspected to be related to zoledronic acid or placebo)
4. Seriousness (serious/non-serious)
5. Expectedness (expected/unexpected) (applicable only if the event is suspected to be causally related to zoledronic acid or placebo)
6. Actions taken
7. Outcome

The severity of the adverse event (e.g., mild, moderate, or severe) will not be recorded because this information is not legally required and is unlikely to be analyzed.

Participants who have been affected by an AE will be followed-up according to the clinical practice of the study center until the adverse event is resolved or stable. Participants with AEs that are suspected to be related to the investigational product will be followed-up until they have recovered or are well taken care of and on the way to good recovery.

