8.2. Serious adverse events

As recommended by the ICH,⁵⁰ an adverse event will be classified as a *serious adverse event* if it

- *results in death,*
- *is life-threatening,*
- *requires inpatient hospitalization or prolongation of existing hospitalization, or*
- *results in persistent or significant disability or incapacity.*

As also stated by the ICH,⁵⁰

Study Name: The Fragility Fracture Trial
Version No: 2
Date: 2020-10-04
EudraCT No: 2019-004766-17

Medical and scientific judgement should be exercised in deciding whether expedited reporting is appropriate in other situations, such as important medical events that may not be immediately life-threatening or result in death or hospitalisation but may jeopardise the patient or may require intervention to prevent one of the other outcomes listed in the definition above. These should also usually be considered serious.

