12.2. Electronic case report forms

The data required to be collected according to this protocol will be entered by investigators onto eCRFs, which will be pseudo-anonymized with participant ID codes. There are two exceptions to this rule, however. First, pseudo-anonymized accelerometer data will be sent to the sponsor for central wear-time validation and physical activity scoring. Second, registry-data will be collected centrally by the sponsor.

All efficacy outcomes and adverse events will be recorded using the ICD-10-SE system. Medications will be recorded using the Anatomical Therapeutic Chemical Classification System. The eCRF has not been created at the time of writing, but once this is done, its location will be specified in subsequent versions of this protocol or in the Clinical Study Report. To ensure that the system is secure, the eCRF system will be set up in collaboration with the University Hospital of Umeå Clinical Research Centre and the Department of ICT Services and System Development at Umeå University.

Investigators must ensure that eCRFs are correct and complete and that reporting takes place within the predefined time windows. An entry on the eCRF should be marked ND (Not done) if the information was not collected, NK (not known) if the information is unknown, and NA (not applicable) if the information does not apply, with appropriate Swedish translations. Any corrections made to an eCRF should be noted, signed, dated, and (if needed) explained.

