13.7. Safety analysis

All participants who receive at least one infusion will be included in a safety analysis. The occurrence of adverse events by the end of follow-up will be analyzed as the number of events and the number and percent of participants reporting at least one event. These data will

Study Name: The Fragility Fracture Trial
Version No: 2
Date: 2020-10-04
EudraCT No: 2019-004766-17

be presented by study group, seriousness, and causality (suspected/not suspected relation to study medication). The study groups will be compared using Fisher's exact test. For post-infusion symptoms occurring ≤ 3 days after infusion, data will be presented for both infusions in total and for events reported to have occurred ≤ 3 days after each infusion. In addition to specific adverse events, the composite safety outcomes of any adverse event, any serious adverse event, any serious adverse drug reaction, any unexpected adverse drug reaction, and any suspected unexpected serious adverse reaction will be reported. Laboratory values of serum calcium (low, <2.2 mmol/l; normal, 2.2-2.6; high, >2.6)⁶² will be analyzed in a shift table from before the first to before the second infusion. The number and percent with severe renal impairment (estimated glomerular filtration rate <35 ml/min/1.73m²) at Follow-Up Visit 1 will be presented. The mean and standard deviation change in estimated glomerular filtration rate from before the first to before the second infusion will be presented and compared between the groups using an independent-samples *t* test (Satterthwaite approximation of degrees of freedom).

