Co-authorship of the peer-reviewed journal article will be determined based on the recommendations of the International Committee of Medical Journal Editors.⁷³ After the end of the trial, the principal investigators and the sponsor/coordinating investigator will each make a list of members of their staff who want to be included as authors. These lists must include a statement of which ICMJE criteria for apply to each name on the list, as well as an explanation of how each person meets the criteria. The investigators and the sponsor will jointly assess who on these lists meet the ICMJE criteria. The investigators and the sponsor will also determine the order in which the names will appear in the published article. The final decision of which names will appear and in what order will be the joint decision of all investigators, by consensus if possible, by majority vote if necessary. The sponsor will break a tie should one arise.

17. Risk-benefit evaluation

The main expected benefit of zoledronic acid is a reduced risk of fractures. Based on previous studies, we expect to see a 35% relative risk reduction, corresponding to a 3.5% absolute risk reduction. There are also health economics benefits to consider. Below is an example for hip fractures.

We expect hip fractures to occur in approximately 5% of participants during follow up. With an absolute risk reduction of 1.75% from zoledronic acid (35% relative risk reduction), the numbered need to treat to avoid 1 hip fracture is 57. In clinical practice, the cost of the study drug (two 5 mg infusions of zoledronic acid) is about 300 Swedish Krona (SEK). Additional costs of treatment (e.g., the cost of personnel and blood tests) amount to approximately 500 SEK, meaning that the total cost of treatment is about 800 SEK. Therefore, the estimated cost to avoid one hip fracture is $800 \times 57 = 45,600$ SEK.

This cost of 45,600 SEK can be compared to the estimated hospitalization cost of 100,000 SEK for each hip fracture patient.⁷⁴ Furthermore, in the 12 months following the fracture, each hip fracture patient requires subsequent health care and social care for about 400,000 SEK.⁷⁴ Thus, there are substantial health economic benefits based only on hip fractures. We expect further cost benefits due to reductions in other types of fractures and increased quality-adjusted life years.

Study Name: The Fragility Fracture Trial
Version No: 2
Date: 2020-10-04
EudraCT No: 2019-004766-17

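### The composite of any serious adverse event takes in hospitalized fractures that zoledronic acid is expected to prevent, and no version without them is planned

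*Protocol*

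**What the plan says.** Section 8.1 takes over the ICH definition of an adverse event: "Any untoward medical occurrence in a patient or clinical investigation subject administered a pharmaceutical product", with or without a causal link. Section 8.2 makes an event serious if, among other criteria, it "requires inpatient hospitalization or prolongation of existing hospitalization". Neither section exempts the trial's efficacy outcomes.

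The risk-benefit evaluation in Section 17 budgets an "estimated hospitalization cost of 100,000 SEK for each hip fracture patient", so the protocol itself treats hip fractures as admissions.

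Section 13.7 presents adverse events by arm, seriousness and suspected causality, and "The study groups will be compared using Fisher's exact test". Alongside the specific events it adds "the composite safety outcomes of any adverse event, any serious adverse event, any serious adverse drug reaction" and two other composites. No composite is planned with fractures left out.

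Whether one event can be both an efficacy outcome and an adverse event is not stated. Section 12.2 says that "All efficacy outcomes and adverse events will be recorded using the ICD-10-SE system", and Table 1 has separate rows for outcome assessment and adverse event assessment. Neither says that one category excludes the other.

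**The concern.** A safety composite should move with harm. On the protocol's definitions this one also moves with efficacy: if zoledronic acid prevents hip fractures, fewer participants on it will have any serious adverse event, whatever else the drug does. A finding of no difference could then mean either no harm, or fewer fractures offset by more of something else.

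Specific-event rows show an excess that falls in one diagnosis. An excess spread thinly over many diagnoses is what an overall composite is meant to pick up, and that is where the offset matters. Severity is not recorded (Section 8.1), so seriousness is the only grading available for an overall comparison.

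**Working it through.** **Inputs from the protocol.** 2900 participants, 1:1, so 1450 per arm. Hip fracture on placebo 457/10,361 = 4.4%, with a 34% reduction (Section 13.10). Alternatively, hip fracture about 5% with an absolute reduction of 1.75 points, giving 3.25% (Section 17). All clinical fractures 10% v 6.62% (Appendix 1).

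**Assumptions not in the protocol.** Other serious events occur in b = 20%, 30% or 40% of placebo participants over 4 years, independently of fracture. A 5-point excess on zoledronic acid serves as the test case.

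**Reproducing the plan's hip figure.** Risk on zoledronic acid = 1 − (1 − 0.0441)^0.66 = 0.0293. Events = 2900 × 0.95 × (0.0441 + 0.0293)/2 = 101. Power = Φ(√(101.2/4) × |ln 0.66| − 1.96) = Φ(0.13) = 55%. This agrees with Section 13.10, so 4.4% v 2.9% is the plan's own expectation.

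**Shift with no other effect.** With hip fracture risk f, P(any serious event) = 1 − (1 − f)(1 − b), so the arms differ by (f0 − f1)(1 − b).
- 4.4% v 2.93%: 1.47 × 0.8, 0.7, 0.6 = 1.2, 1.0, 0.9 points lower on zoledronic acid.
- 5% v 3.25%: 1.75 × 0.8, 0.7, 0.6 = 1.4, 1.2, 1.05 points lower.

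**Excess exactly cancelled.** (f0 − f1)(1 − b)/(1 − f1) gives 0.9 to 1.5 points over the same range, or about 13 to 21 participants per 1450.

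**Power for a 5-point excess of other serious events.** Two-sided 5% level, normal approximation to the planned Fisher test: power = Φ((d − 1.96·SE0)/SE1), where SE0 is pooled and SE1 unpooled.

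Worked at b = 30%:
- Without fractures, 30% v 35%: SE0 = SE1 = 0.0174, so Φ((0.050 − 0.0341)/0.0174) = 82%.
- With hip fractures (4.4% v 2.93%), the composites are 33.1% v 36.9% and d = 0.0382: Φ((0.0382 − 0.0347)/0.0177) = 58%.

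| Background b | Without fractures | Hip 4.4% v 2.9% | Hip 5% v 3.25% |
|---|---|---|---|
| 20% | 90% | 62% | 56% |
| 30% | 82% | 58% | 53% |
| 40% | 78% | 58% | 54% |

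**Upper bound.** If every clinical fracture were serious (10% v 6.62%), power would be 21-30%. Many arm fractures will not need admission, so this is a limit and not an expectation.

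**The all-adverse-event composite.** At an assumed background of 80-90%, even counting all clinical fractures, the shift is 3.38 × 0.2 to 3.38 × 0.1 = 0.7 to 0.3 points. Section 2 expects post-infusion symptoms in about a third of patients after the first infusion, which pushes this composite the other way.

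**The case against.** **Inclusion is inferred.** The protocol never says that fractures are entered as adverse events. Adverse events are sought with open questions and fractures are asked about separately, so the two may have been meant to stay apart. This stands as an ambiguity. As written, though, the definitions cover a hospitalized fracture and no text takes it out.

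**An all-inclusive composite is legitimate, and table layout belongs to the analysis plan.** The composite does follow the ICH definition, and the proposal keeps it. But Section 13.7 itself fixes the composites and their test, so the issue arises from what the protocol states.

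**Harm would be visible elsewhere.** A reader might infer that the expected benefit hides serious harm altogether. The protocol does not support that. Specific adverse events and eleven pre-specified safety outcomes are shown by arm, deaths, cardiovascular events and cancers are analyzed as secondary outcomes, and the composites limited to suspected reactions would rarely contain an ordinary fracture. Nor does Section 13.7 rank the serious-event composite above the other safety results. The lack of a monitoring board does not alter this, since a board would act during the trial and not on the final table.

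**The all-adverse-event composite.** A reader might extend the argument to it. The arithmetic above shows no material effect.

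**The size rests on assumptions.** True: background rate, independence and the 5-point excess are all assumed. If frail participants have both hip fractures and other serious events, the offset is smaller. Dropping fractures also does little for the very small excess that would be cancelled exactly: over backgrounds of 10-50%, with a 35% reduction in hip fracture, that excess is 0.8 to 1.6 points and the comparison without fractures has only about 6-29% power for it. The gain is for moderate excesses.

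**Conclusion.** The point holds for the composite of any serious adverse event, and only there. On the protocol's hip fracture expectations the composite is tilted by about 0.9 to 1.4 points in favor of zoledronic acid, and power for a 5-point excess of other serious events drops from 78-90% to about 53-62%. This rests on an assumed 20-40% background, on independence, and on hip fractures being the only serious fractures. Other admitted fractures would enlarge the effect, and positive correlation with other serious events would shrink it.

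A reader might go further and rest the whole safety conclusion on a version without fractures. The protocol gives no ground for that. Section 7.1 covers all of S72, while Section 7.4 lists atypical femur fracture as a safety outcome and traces femur shaft fractures by codes within S72. Removing every Section 7.1 fracture would take a recognized harm out of the count. The two versions should be read together. The change is worth making, because it is cheap and the data are already collected.

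**What to change.** In Section 13.7:

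1. State that efficacy fractures count as adverse events, and as serious ones when they meet Section 8.2.
2. Report and compare the composite of any serious adverse event twice: over all events, and excluding clinical fractures as defined in Section 7.1. Atypical femur fracture, death, myocardial infarction, stroke and cancer stay in both versions. Some of these are also hoped-for benefits (Section 3.2), but they are events that a count of serious harm has to keep.
3. State that the two versions will be interpreted side by side.

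The all-adverse-event composite needs no second version. The cost is a sentence or two, one extra table row and one extra comparison without multiplicity adjustment. No new data are needed.

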13.8. Subgroup, sensitivity, and exploratory analyses

Baseline characteristics and efficacy outcomes will be presented in subgroups defined by type of baseline fragility fracture (grouped by the first 3 characters of ICD-10-SE codes), age (65-74, 75-84, or ≥ 85 year), sex, study center, and FRAX 10-year probability of major osteoporotic fracture. In the efficacy analysis, product terms will be included in regression models to assess interaction of treatment with time since fragility fracture, type of fragility fracture, age, sex, study center, physical activity (mean steps/day), and receipt of one or both infusions. These interaction effects will be tested using Wald tests for numeric and binary variables and likelihood ratio tests for multi-level categorical variables. We do not expect these interaction analyses to show significant differences in effect.

Six sensitivity analyses will be conducted. First, to assess the presence of confounding, regression analyses will be adjusted for the following baseline covariates: age, sex, BMI, study center, time since fragility fracture, and site of fragility fracture (grouped by the first 3 characters of ICD-10-SE code). Second, the efficacy analysis will be rerun in a per-protocol population (i.e., participants who met all eligibility criteria, either died or completed follow-up, and both were qualified to receive and did receive the 2 assigned infusions). Third, efficacy concerning time-to-event outcomes will be analyzed using the Andersen-Gill Cox model for recurrent events.⁶³ Fourth, in the analysis of the primary outcome, the potential effect of informative censoring (including the competing risk of death) will be assessed by rerunning Cox models under the extreme scenarios that all participants who did not complete follow-up either (1) sustained a fracture at the time of censoring (i.e., were at high risk of fracture) or (2) had complete follow-up with no event (i.e., were at low risk of fracture).⁶⁴ Fifth, participants with a history of cancer at baseline will be excluded from the efficacy analysis of new cancers diagnosed during follow-up. Sixth, outcome events not verified by medical records will be included in the efficacy analyses.

Study Name: The Fragility Fracture Trial
Version No: 2
Date: 2020-10-04
EudraCT No: 2019-004766-17

To assess the time-to-onset of treatment effect on the primary outcome, Kaplan-Meier curves will be compared using the log-rank test with censoring at months 48, 42, 36, and so on until month 6. To avoid the problem of multiple testing, a fixed-sequence procedure will be used in which the test will first be performed for risk at month 48, then at month 42, and so on until month 6.⁶⁵ If a p-value ≥ 0.05 is obtained, the results of all subsequent tests will also be considered non-significant. Similarly, Cox regression will be used to estimate hazard ratios and 95% confidence intervals, with censoring at month 48, 42, and so on until month 6.

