3.3. Exploratory objectives

The exploratory objectives are as follows:

1. To investigate whether the effect of zoledronic acid on new clinical fracture decreases with age
2. To investigate the time-to-onset of effect of zoledronic acid on clinical fractures
3. To investigate whether a higher level of physical activity leads to a greater reduction in clinical fractures with zoledronic acid
4. To investigate whether zoledronic increases muscle strength, as compared with placebo
5. To investigate whether the effect of zoledronic acid on new clinical fractures is greater in participants who have a higher 10-year probability of major osteoporotic fracture according to the FRAX fracture risk assessment tool
6. To investigate whether zoledronic acid reduces height loss, as compared with placebo
7. To investigate whether zoledronic acid improves health-related quality of life
8. To investigate whether zoledronic acid reduces the risk of death, cancer, clinical fractures, and cardiovascular disease, as compared with placebo, over 10 years

Efficacy by age was selected as an exploratory objective because some researchers suggest that bone-protective therapy is less effective in the oldest age groups, perhaps because the high incidence of falls offsets beneficial skeletal effects.^{32,33} Low treatment rates of osteoporosis have also been observed in the oldest age groups.³⁴ Efficacy by level of physical activity was selected because it is well known that bone-protective agents have different effects on bone mineral density in different individuals. Given that physical loading decreases the risk of fractures and is necessary for maintaining bone health at all ages,³⁵ we hypothesize that zoledronic acid will result in a greater increase in bone density, and therefore a greater decrease in fracture risk, in participants who are physically active. Muscle strength is included as an explanatory outcome because it is a possible mechanism for a beneficial effect of zoledronic acid on falls. This mechanism is supported by the known crosstalk between osteocytes and muscle cells, which is mediated by pathways influenced by bone-protective

Study Name: The Fragility Fracture Trial
Version No: 2
Date: 2020-10-04
EudraCT No: 2019-004766-17

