6.1. Discontinuation of treatment

The investigators and the sponsor can at any time decide that a participant should not have the second infusion due to, for example, adverse events. A participant will be automatically disqualified from receiving the second infusion if any one of the following criteria is met:

1. Decision of investigator or sponsor
2. Request from participant
3. Withdrawal of the participant from the trial
4. Initiation of bone-protective therapy (other than the assigned investigational product)
5. Severe renal impairment (estimated glomerular filtration rate of <35 ml per minute per 1.73 m² of body surface area) at Follow-Up Visit 1
6. Hypocalcemia (serum calcium <2.2 mmol/L) at Follow-Up Visit 1, unless this can be resolved within the time window of the second infusion, i.e., 24 months ± 4 weeks (see Section 9)

A participant's follow-up will continue even if treatment is discontinued, unless the participant wishes to withdraw from the study.

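### Section 13.8 tests a treatment interaction with receipt of one or both infusions, a post-randomization variable, and gives no interaction term for FRAX, although an exploratory objective asks for it

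*Protocol*

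**What the plan says.** Protocol Section 13.8 states for the efficacy analyses that "product terms will be included in regression models to assess interaction of treatment with time since fragility fracture, type of fragility fracture", and the list continues with "age, sex, study center, physical activity (mean steps/day), and receipt of one or both infusions". In the sentence before, the variables by which results will be presented in subgroups end with "study center, and FRAX 10-year probability of major osteoporotic fracture". FRAX is therefore a presentation subgroup, without stated cut-points, and has no product term.

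Exploratory objective 5 (Section 3.3) asks whether the treatment effect "is greater in participants who have a higher 10-year probability of major osteoporotic fracture according to the FRAX fracture risk assessment tool".

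Section 6 places the second infusion at 2 years. Section 13.6 counts survival time from randomization. Section 6.1 bars the second infusion for several reasons, among them withdrawal, a decision by investigator or participant, and "Initiation of bone-protective therapy (other than the assigned investigational product"). Section 5.2 says that hip and vertebral fracture patients should receive such therapy under national guidelines.

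The per-protocol population in 13.8, used for the second of six sensitivity analyses, is limited to eligible participants who "either died or completed follow-up, and both were qualified to receive and did receive the 2 assigned infusions".

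**The concern.** Every other variable in the interaction list is known at randomization. Receipt of one or both infusions is decided by what happens in the following two years, and some of those events are the outcomes being analysed.

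- **Death.** Anyone who dies before month 24 is in the one-infusion group. Time to death is a secondary efficacy outcome, so if the list is applied to it, all early deaths fall in one stratum and none in the other.
- **Fracture.** A primary-outcome fracture before month 24 can start bone-protective therapy, which disqualifies the participant from the second infusion.
- **Other loss.** Refusal, withdrawal, renal impairment and hypocalcemia may occur at different rates in the two arms.

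If this other loss differs by arm, the one-infusion groups are mixed differently in each arm, and a constant drug effect can look like a stronger effect after one infusion. That would be an awkward false lead in a trial whose two-year interval is itself non-standard (Section 6). The change history for version 2 shows that the one-versus-two-infusion objective was removed because such a comparison may be biased, and Section 3.3 no longer contains it. The point does not depend on that history.

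Meanwhile, the effect modification that objective 5 does ask about has no product term, although age, sex and physical activity each have one.

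**Working it through.** **1. The plan's own figures.** Schoenfeld events for HR 0.65, 90% power and two-sided 5%: 227. Risk on zoledronic acid: 1 − 0.9^0.65 = 0.06619. Participants: 227 / ((0.10 + 0.06619)/2) = 2732, and 2732/0.95 = 2876, rounded up to 2900. All reproduce. None is in dispute.

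**2. How many events come before the second infusion.** With constant hazards, 1450 per arm and 5% dropout (1450 × 0.95 = 1377.5 per arm):
- placebo: 1 − 0.9^0.5 = 0.0513, giving 71 events by month 24
- zoledronic acid: 1 − 0.9^0.325 = 0.0337, giving 46 events
- total 117 of about 229 expected events, or 51%

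In the source cohort of Section 13.10, (457 + 91)/1028 = 53% of new fractures were of the hip or lumbar spine. If that share holds and each led to therapy, about 0.53 × 117 = 62 early fractures would be placed in the one-infusion group.

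**3. Why equal loss does little harm and unequal loss does more.** Assume that half of early fracturers lose infusion 2, that all others lose it at a rate r, and that the true HR is 0.65 throughout (4-year risk ratio 0.06619/0.10 = 0.66).

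One-infusion group, share with a fracture:
- placebo, r = 10%: (0.0513×0.5 + 0.0487×0.10) / (0.0513×0.5 + 0.9487×0.10) = 0.0305/0.1205 = 25.3%
- zoledronic acid, r = 10%: (0.0337×0.5 + 0.0325×0.10) / (0.0337×0.5 + 0.9663×0.10) = 0.0201/0.1135 = 17.7%
- zoledronic acid, r = 20%: (0.0337×0.5 + 0.0325×0.20) / (0.0337×0.5 + 0.9663×0.20) = 0.0233/0.2101 = 11.1%

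The risk ratio with one infusion is 17.7/25.3 = 0.70 under equal loss, close to the truth, but 11.1/25.3 = 0.44 when loss is 10% versus 20%. The extra event-free participants on active drug dilute that arm's one-infusion group.

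**4. Cox fits in a large simulated cohort (300,000), same true HR of 0.65.**
- Equal other loss (5 to 10%), with 10 to 80% of early fracturers losing infusion 2: stratum HRs 0.63 to 0.67.
- Other loss 10% versus 15 to 20%, with 50% of early fracturers losing it: 0.48 to 0.40 with one infusion, 0.66 to 0.67 with both. The expected |z| for interaction is 1.1 to 1.9.
- No drug effect (HR 1.0), same unequal losses: 0.73 to 0.60 with one infusion, 1.03 to 1.05 with both. The expected |z| is 1.4 to 2.2.

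**5. False-positive rate of the interaction test in trials of 2900.** Assumptions: true HR 0.65, 10% four-year mortality, hip/vertebral share 548/1028. Ranges reflect separate runs with Cox models or rate ratios.

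| Decline of infusion 2, placebo vs active | Hip/vertebral fractures leading to therapy | Falsely significant |
|---|---|---|
| equal | 80% | 5–6% |
| 10% vs 12% | 80% | 6% |
| 5% vs 7% | 80% | 8% |
| 5% vs 15% | 10% | 7% |
| 5% vs 15% | 30% | 19% |
| 10% vs 20% | 80% | 23–27% |
| 5% vs 15% | 80% | 49–57% |

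In the last row the HR is about 0.35 to 0.37 with one infusion and 0.65 with both.

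**6. FRAX, side by side.** The objective is "To investigate whether the effect of zoledronic acid on new clinical fractures is greater in participants who have a higher 10-year probability". The subgroup sentence in 13.8 includes FRAX; the product-term list does not. FRAX is already collected (numeric baseline variables 22 and 23 in Section 13.2).

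**The case against.** The strongest reply is about size. The documents give no rate of decline, no mortality and no rate at which an in-trial fracture leads to therapy. The highest figure needs decline three times as frequent on active drug together with 80% therapy. The protocol describes post-infusion symptoms as transient and less common after later infusions, the trial is double-blind, and its only uptake figure is around 10% of fracture patients (all fracture types). Under milder inputs the false-positive rate is 6 to 8%. This stands: the result is a range, not an expected failure. It does not rescue the term, which supports no current objective and misbehaves just when loss differs by arm.

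Three stronger readings are tempting but not supported:
- **That membership is simply driven by the outcome.** Fracture is not a disqualifier in Section 6.1. A participant with an early fracture who does not start other therapy can still receive infusion 2. Dependence is partial, except for death.
- **That the per-protocol analysis is shown to be biased and must be rebuilt with weights.** It does lose events: 21 to 34% of first fractures under the assumptions in step 5 of the working. Yet the both-infusions HR stays at 0.64 to 0.66 in that model and reaches at most 0.67 in the step 4 simulation, against a truth of 0.65. Lost events are not bias, and the analysis is labelled as a sensitivity analysis.
- **That FRAX is absent.** It is presented by subgroup, so objective 5 is addressed descriptively. An unseen statistical analysis plan could add a test. Even so, the protocol itself fixes an explicit list that leaves out the one modifier this objective needs.

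**Conclusion.** The point holds as a minor-to-moderate defect in Section 13.8. Receipt of one or both infusions is a post-randomization variable and does not belong in a list of treatment interactions analysed from randomization. The distortion is negligible if loss of the second infusion is equal by arm (5 to 6% false positives). It grows with the difference between arms and with the share of early hip and vertebral fractures leading to therapy, up to about 50 to 60% in the most unfavourable case examined. All loss, mortality and therapy rates are assumptions. For time to death the dependence needs no assumption.

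The FRAX omission is a plain mismatch between objective 5 and the product-term list.

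A reader might infer that the trial's main conclusion is at risk. It is not: the primary log-rank test compares groups as randomized, and the events, sample size and power are unchanged.

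**What to change.** In the product-term list of Section 13.8:
1. Delete receipt of one or both infusions. If some view of it is wanted, replace it with a landmark analysis starting at month 24, labelled descriptive.
2. Add the FRAX 10-year probability of major osteoporotic fracture as a continuous variable.

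For the per-protocol population, whose definition requires that participants "both were qualified to receive and did receive the 2 assigned infusions", add one sentence saying that the analysis conditions on surviving to and receiving the second infusion and is supportive only. A weighted redesign is not required.

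The cost is a few lines of wording and minor programming. FRAX is already a baseline variable, so no new data are needed, and the sample size stays at 2900.
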